Sample size rationale: With the expansion of recruitment of patients with a Heath Status score of 3 or 4 at baseline, an informed sample size calculation has been carried out using the observed effect size in the pilot portion of the study (with n=148 patients) for the updated Primary Efficacy Endpoint "The proportion of patients requiring mechanical ventilation AND/OR deceased by Day 60", the observed rate of patients withdrawing consent to be followed up.

Statistical Analysis

Using the proportion of patients requiring invasive mechanical ventilation AND/OR deceased by Day 60 in the pilot portion of the study, an effect size of 7% change (i.e. 7% in the control group vs. 0% in the investigational group), comparing the active arm versus the control (placebo) arm, and a minimum of 90% statistical power of detecting a difference in proportions of 7% as statistically significant using a two-tailed Fisher Exact test with a nominal alpha of 0.05 (5%), a total sample size of 264 patients (132 per arm) with a Heath Status score of 3 or 4 at baseline is required.

To ensure the study is powered adequately if the effect size is smaller than initially estimated, an interim sample size re-estimation (Mehta and Pocock, 2011)⁸⁵ including a futility analysis will occur once 42% (112) of the planned 264 patients have either completed the Day 60 primary endpoint assessment or terminated their study participation early. If the conditional power is within the promising zone, the sample size may be increased up to a maximum of 462 patients, dependent upon the results of the interim sample size re-estimation. If the conditional power is below the promising zone, the futility criteria will be deemed met and a recommendation to stop further enrollment will be communicated to the DSMB and the Sponsor.

Primary Efficacy Endpoint Analysis:

The primary hypothesis test will be based on a test of a null hypothesis that the proportions of patients requiring mechanical ventilation OR deceased by Day 60 for the two treatment groups are the same against the alternative hypothesis that the investigational group is superior to the control group. The statistical analyses for the other study parameters are summarized in the Statistical Analysis, Section 12, and will be detailed in the SAP.

SCHEDULE OF EVENTS

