In subgroups 3 and/or 4 (and the combined 3+4 subgroup as well) LAU-7b plus standard of care showed a 100% reduction in the risk of all-causes death and the risk of progressing to invasive mechanical ventilation by Day 60, when compared to placebo plus standard of care, as well as an improvement in the proportion of patients alive and without respiratory failure at Day 29, a faster recovery and shorter hospitalization.

More specifically, none of the 76 moderately to severely ill COVID-19 patients treated with LAU-7b died or progressed to mechanical ventilation, while 4 patients died (4/72, 5.6%, p=0.053) and 5 progressed to mechanical ventilation (5/72, 6.9%, p=0.025) in the placebo arm. For some endpoints, the positive trend is more evident in subgroup 3 while for others, it is subgroup 4 which shows the higher benefit. Combining them increases the sample size and approaches statistical significance. This is indicative that the combined 3+4 population should be studied further to confirm the results above. This positive signal, in particular the total prevention of the need for mechanical ventilation or mortality in subgroups 3 and 4, was recognized by clinicians as being clinically relevant and worthy of clinical confirmation for this particularly underserved hospitalized population. Avoiding at all costs the progression toward respiratory failure and the need for ICU and invasive mechanical ventilation is a high priority.

The subgroup analysis of critically ill COVID-19 patients didn't show an improvement in the LAU-7b arm over placebo, suggesting that patients already in respiratory failure at baseline may be too severely affected by the disease to benefit from LAU-7b treatment.

Summary:

In conclusion, patients that were not in respiratory failure at baseline (Moderate-to-Severe COVID, Health Status 3 and 4) responded positively to treatment with LAU-7b, supporting further evaluation in this patient subset. Safety was excellent in the overall Safety population and particularly in the Moderate-to-Severe COVID patients.

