12.1 Sample Size Determination

The main efficacy variable is the 7-point Ordinal Scale of the patient Health Status and the primary efficacy endpoint is the proportion of patients requiring mechanical ventilation and/or deceased (ordinal scale scores 6-7 inclusively) by Day 60 compared between the active and control (placebo) arms of the study. The sample size has been formally estimated for this revised primary efficacy endpoint, in the view of confirming the positive signals of efficacy obtained during the pilot portion of the trial (see Section 5.4.2.1 for a summary of these results.

The study showed so far that patients with a Health Status of 3 or 4 at baseline benefited from LAU-7b therapy while patients with a Health Status of 5 at baseline (with an established respiratory failure) were apparently too advanced to benefit from LAU-7b therapy. Therefore, going forward with this expansion, the enrolment will focus only on patients with a Health Status of 3 or 4 at baseline. The observed effect size for the revised primary efficacy endpoint in the pooled patients with a Health Status score of 3 or 4 at baseline in the pilot portion of the study (n=148) was 7% (0% in the LAU-7b arm, 6.9% in the placebo arm).

A target of circa 264 SARS-CoV-2 positive patients with a Heath Status score of 3 or 4 at baseline total sample size are therefore required in the Phase 3 portion of this study under the initial assumption of effect size (see below for the sample size re-estimation). Consequently, once additional enrolment is completed, a minimum of 412 patients with a Heath Status score of 3 or 4 at baseline will have been randomized in this study, for a total 496 patients including the 84 patients with a Health Status score of 5 enrolled during the Phase 2 pilot portion.

Sample size rationale: Based on the WHO Master Protocol ⁸⁶, utilization of the main efficacy variable that uses an ordinal severity scale with 7 categories, enables the calculation of numerous study endpoints including the primary efficacy endpoint, the proportion of patients requiring mechanical ventilation AND/OR deceased by Day 60. The primary hypothesis test will be based on a test of a null hypothesis that the proportions of patients requiring mechanical ventilation AND/OR deceased by Day 60 for the two treatment groups are the same against the alternative hypothesis that the investigational group is superior to the control group.

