Using the proportion of patients requiring mechanical ventilation AND/OR deceased by Day 60 in the pilot portion of the study, an effect size of 7% change (i.e. 7% in the control group vs. 0% in the investigational group), comparing the active arm versus the control (placebo) arm, and a minimum of 90% statistical power of detecting a difference of 7% using a two-tailed Fisher Exact test, with a nominal alpha of 0.05, a total sample size of 264 patients (132 per arm) with a Heath Status score of 3 or 4 at baseline is required for the Phase 3 confirmatory portion of this study.

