Population-Level Summary	The proportion of patients requiring mechanical ventilation (includes ECMO) AND/OR deceased by Day 60 will be analyzed using a Fisher		

	exact test to compare proportion of LAU-7b treated subjects relative to placebo.
Estimand Description	Superiority of LAU-7b on the proportion of patients requiring mechanical ventilation or deceased by Day 60 will be analyzed using Fisher exact test irrespectively from the interruption of treatment, early discontinuation of the treatment (for other reason than death) or use of disallowed medication.
Imputation/Data/Censoring Rule(s)	Missing observations will be treated as a non-response (i.e. patient considered as Health Status 6-7 inclusively) for the primary analyses on ITT.
Sensitivity Analysis	Sensitivity analyses where missing observations will be imputed using different methods will also be performed and will be further detailed in the SAP.

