12.7 Efficacy Analysis

12.7.1 Analysis of Primary Endpoint

The proportion of patients requiring mechanical ventilation (includes ECMO) AND/OR deceased by Day 60 will be analyzed using a Chi-Square test (or a Fisher exact test if the expected values in any of the cells of the contingency table are below 5).

Logistic regression including treatment group, age group and other prognostic factors at baseline will also be performed.

Missing observations will be treated as a non-response (i.e. patient not considered as alive and free of respiratory failure) for the primary analyses on ITT. Sensitivity analyses where missing observations will be imputed using different methods will also be performed and will be further detailed in the SAP.

Additional post-hoc analyses may be performed in an exploratory manner depending on the frequency of other phenotypes or concomitant drugs.

Full details will be specified in the SAP and its Addendum dedicated to the study expansion.

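### The 90% design power holds only if no Day 60 outcome is missing on LAU-7b; under the protocol's missing-equals-failure rule, an assumed 1% to 2% missing in both arms cuts it to 73% to 61% (Fisher)

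*Protocol*

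**What the plan says.** Section 12.1 of the protocol plans on "an effect size of 7% change (i.e. 7% in the control group vs. 0% in the investigational group") and claims "a minimum of 90% statistical power of detecting a difference of 7% using a two-tailed Fisher Exact test" at a nominal alpha of 0.05, with 264 patients (132 per arm). The synopsis repeats the claim: "a minimum of 90% statistical power of detecting a difference in proportions of 7% as statistically significant". The rates come from the pilot patients with Health Status 3 or 4. Section 12.1 reports that the effect "was 7% (0% in the LAU-7b arm, 6.9% in the placebo arm"), and Section 5.4.2.1 that "none of the 76 moderately to severely ill COVID-19 patients treated with LAU-7b died or progressed to mechanical ventilation", against 5 of 72 ventilated on placebo.

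The analysis differs from the planning model. Table 3 in Section 12.4 says: "Missing observations will be treated as a non-response (i.e. patient considered as Health Status 6-7 inclusively) for the primary analyses on ITT". Section 12.7.1 also treats missing outcomes as non-response. Table 3 names Fisher's test alone, whereas under Section 12.7.1 the endpoint is "analyzed using a Chi-Square test (or a Fisher exact test if the expected values in any of the cells" fall below 5). Section 8.4 does not replace patients who withdraw after randomization.

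The synopsis lists "the observed rate of patients withdrawing consent to be followed up" at the end of its description of the sample size inputs, but gives neither the rate nor its use. Section 12.2 allows up to 231 per arm, tied to 4% vs 0% at 90% power.

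The SAP addendum (Sections 1 and 2), written after the results were released on 14MAR2024, makes a complete-case analysis primary and keeps the imputed analysis in the CSR under a different label.

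**The concern.** A planning rate of exactly 0% leaves no room for imputed failures. The pilot's 0 of 76 counts observed deaths and ventilations. The planned primary analysis counts those plus every missing Day 60 outcome. The two agree on LAU-7b only if nobody in that arm is missing.

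With so few events, a single imputed failure moves the rejection boundary by two placebo events. The power quoted in the synopsis and in Section 12.1, and the 90% attached to the 462 cap in Section 12.2, may therefore not belong to the analysis the protocol specifies. Anyone who reads the superseded imputed analysis in the CSR against a 90% design power would take it to have been better powered than it was.

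**Working it through.** **Inputs.** From the protocol: 132 per arm; true event rates 7% (placebo) and 0% (LAU-7b); two-sided 0.05; Fisher's test (12.1, Table 3) or the 12.7.1 rule, read here as Pearson chi-square without continuity correction when all expected counts are at least 5 and Fisher otherwise; missing = failure. Assumed, because the documents give no figure: a missing rate *m*, independent of outcome. All powers come from exact enumeration of two binomials, counting rejections in favour of LAU-7b.

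**1. The plan's own figure.** With a LAU-7b rate of 0%, the LAU-7b count is always 0. Fisher p-values (placebo vs LAU-7b failures): 5 vs 0, 0.0601; 6 vs 0, 0.0295. So six placebo failures are needed:

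P(Bin(132, 0.07) ≥ 6) = 90.6%.

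The stated 90% is reproduced. At 131 per arm the result is 90.3% and at 130 per arm 89.9%, so 132 carries no visible allowance for missing outcomes.

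**2. Rates under missing = failure.** LAU-7b: *m*. Placebo: *m* + (1 − *m*) × 0.07.
- *m* = 1%: 1.00% vs 0.01 + 0.99 × 0.07 = 7.93%
- *m* = 2%: 2.00% vs 0.02 + 0.98 × 0.07 = 8.86%

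The chance that no LAU-7b outcome is missing is 0.99^132 = 26.5% at 1% and 0.98^132 = 6.9% at 2%.

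**3. Why the loss is large.** Fisher p-values with imputed LAU-7b failures: 7 vs 1, 0.0662; 8 vs 1, 0.0359; 9 vs 2, 0.0600; 10 vs 2, 0.0344. One LAU-7b failure raises the placebo count needed from 6 to 8. (At 9 vs 2 the expected count is 11/2 = 5.5 per arm, so 12.7.1 uses chi-square and p = 0.0311. This is why its power is higher.)

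Fixed numbers missing, Fisher:
- one LAU-7b patient only: P(Bin(132, 0.07) ≥ 8) = 71.2%
- one per arm: P(Bin(131, 0.07) ≥ 7) = 81.8%
- one LAU-7b and two placebo: 89.9%; with three placebo: 95.2%
- one placebo patient only: 95.6%

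**4. Power by missing rate, 132 per arm, missing = failure.**

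| Missing LAU-7b / placebo | Fisher | 12.7.1 test |
|---|---|---|
| 0% / 0% | 90.6% | 90.6% |
| 0.5% / 0.5% | 81.5% | 83.6% |
| 1% / 1% | 73.5% | 79.3% |
| 2% / 2% | 61.1% | 71.4% |
| 5% / 5% | 41.3% | 50.8% |
| 1% / 0% | 62.4% | 68.2% |
| 0% / 1% | 95.5% | 95.5% |
| 1% / 2% | 82.1% | 87.2% |
| 1% / 3% | 88.5% | 92.5% |

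With a Yates correction, the 12.7.1 figures at equal rates of 1% and 2% are the same as Fisher's.

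**5. The cap, 231 per arm.** At 4% vs 0%: 90.3% with complete data; 64.1% (Fisher) and 73.6% (12.7.1) at 1% missing; 50.3% and 59.6% at 2%. At 7% vs 0%: 96.1% and 97.8% at 1%; 89.8% and 92.8% at 2%.

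**6. Complete case (addendum), Fisher, 7% vs 0%.** With both arms reduced equally: 89.9% at 1% missing and 89.5% at 2%. With completer numbers varying at random by arm: 92.2% and 92.0%. These are higher because 5 vs 0 can reach significance when placebo is the smaller arm.

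**The case against.** **The missing rate is assumed.** True. The main SAP (29SEP2023) is not among the documents and may give one, and the synopsis phrase on consent withdrawal stands in a broken sentence. Section 8.3 asks sites for survival and ventilation status to Day 60 even after withdrawal, where local rules permit, and Section 12 keeps patients in follow-up after treatment stops. These measures lower the missing rate but cannot guarantee zero. The addendum shows that missing outcomes mattered enough to change the primary analysis. The finding also does not need a particular rate: one missing patient per arm already gives 81.8%.

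**The exact figures depend on equal arms.** This stands in part. Site-stratified randomization need not give 132/132. With 133 on LAU-7b and 131 on placebo, Fisher power is 95.6% complete, 80.7% at 1% and 68.8% at 2%. With 130 on LAU-7b and 134 on placebo it is 91.3%, 75.1% and 63.3%. The level shifts by several points; the fall does not go away. The same effect of unequal arms explains why the random-completer figures in step 6 exceed 90.6%.

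**Re-estimation could recover the loss.** At 462 patients and 7% vs 0% it largely would, but only trials in the promising zone are enlarged, and imputed failures on LAU-7b push results towards futility. With an assumed conditional power formula (the protocol gives none) and binding futility, overall power at 1% missing is only about 74%.

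**Missingness might favour LAU-7b.** It might: heavier placebo losses raise power, as the table shows. The protocol does not plan on that.

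**It is too late to matter.** Enrolment is over and the size cannot change. That limits the remedy to reporting.

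**Conclusion.** The concern holds. The 90% is correct arithmetic for complete Day 60 outcomes, but it is not a property of the protocol's primary analysis once LAU-7b outcomes are missing, unless placebo losses offset them. At 132 per arm with equal missing rates, power is 73.5% (Fisher) or 79.3% (12.7.1 test) at 1% missing, and 61.1% or 71.4% at 2%. The 90% tied to the cap falls to 64.1% or 73.6% at 1%.

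These sizes rest on an assumed missing rate that is equal by arm and independent of outcome, arms of equal size, a fixed sample size, and an uncorrected chi-square for the 12.7.1 figures. The direction does not depend on the exact rate, and near-equal arm splits change the level by several points only. The point concerns stated power alone; type I error and the treatment estimate are unaffected. Under the addendum's complete-case rule power stays near 90%, but that rule came after the results.

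**What to change.** Wherever the design power is stated (synopsis, Sections 12.1 and 12.2, and now chiefly the CSR), say that the 90% is conditional on complete Day 60 outcomes.

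Add a short table of power against missing rate, under missing = failure and under complete case, for the test actually used. Include equal and unequal rates by arm, a near-equal split such as 131/133, and the 462 cap at both 4% vs 0% and 7% vs 0%.

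Report the pilot missing rate for Health Status 3 and 4 and how it was used, or remove the wording that the withdrawal rate informed the sample size.

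The cost is a few lines and one table. No patients are added and no trial data are re-analysed; the stated power becomes less favourable.

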12.2 Sample Size Re-estimation

To ensure the study is adequately powered, an interim sample size re-estimation/futility analysis is planned for this study, following the procedures proposed by Mehta and Pocock (2011) ⁸⁵. The sample size re-estimation will be performed by one unblinded study statistician, who will not have a decision-making role in the trial. The results will be presented to the DSMB for discussion in the closed session; no one else, including Sponsor or clinical team members, will see the data. When approximately 42% of the subjects have completed the Day 60 primary endpoint assessment or terminated the study, the data are considered "soft-locked" by data management, the data will be provided to the unblinded statistician in the DSMB. The proportion of patients requiring mechanical ventilation AND/OR deceased by Day 60 in each treatment arm will be estimated; and the conditional power (CP) will be calculated.

The maximum allowable sample size is set at 1.75 times the initial sample size (132 × 1.75 = 231 subjects per arm, or 462 in total), corresponding to a difference of 4% (i.e. 4% in the control group vs. 0% in the investigational group) using an alpha of 0.05 and 90% power. Given that the interim analysis is to be performed at 42% of the initial sample size of 264 patients, the targeted power is 90%, and the maximum allowable sample size is 1.75 times, the conditional power cut-off value (CPmin) is calculated as 38.6%. At the interim assessment, if the conditional power (CP), calculated based on the interim data, is between 38.6% and <90% (promising zone), the number of subjects will be increased, up to the maximum allowable sample size for this study. If the conditional power is below the promising zone, the futility criteria will be deemed met and a recommendation to stop further enrollment will be communicated to the DSMB. The communication plan from the DSMB is to report one of the three following statements based on the results: 1) "carry on with the original sample size"; 2) "increase sample size to XXX" or 3) "Stop the study for futility". Details about the DSMB and the data monitoring procedures are specified in the DSMB charter.

Since sample size re-estimation occurs only when the interim conditional power falls in the pre-specified "promising" range, the overall alpha will be protected. Furthermore, because the study will not stop for efficacy regardless of the conditional power, the final analysis will be carried out using conventional tests, without the need for weighing the stage 1 and 2 results or adjusting the alpha value. The operating characteristics obtained from simulation showed that the interim sample size re-estimation approach yields a slightly higher statistical power owing to the slightly higher number of final expected sample size, compared with a classical fixed sample size design.

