To ensure the study is powered adequately if the effect size is smaller than initially estimated, an interim sample size re-estimation (Mehta and Pocock, 2011)⁸⁵ will occur once 42% (112) of the planned 264 patients have either completed the Day 60 primary endpoint assessment or terminated their study participation early. If the conditional power is within the promising zone, the sample size may be increased up to a maximum of 462 patients, dependent upon the results of the interim sample size re-estimation. If the conditional power is

below the promising zone, the futility criteria will be deemed met and a recommendation to stop further enrollment will be communicated to the DSMB and the Sponsor.

7.2.2 **DSMB**

Throughout the study, the DSMB monitors blinded and unblinded safety measures and demographics at regular intervals as specified in the DSMB charter, or as requested by the DSMB chair. The DSMB will receive reports of adverse events by organ class, with emphasis on SAE's, clinically significant adverse events with a high causality potential to the study treatment. Members of the DSMB are not directly involved in the conduct of the study and cannot serve as Investigators in this study.

The DSMB is composed of:

- Three physicians all involved in the care of COVID-19 disease patients, experienced in clinical research, independent of Laurent Pharmaceuticals and not involved as an Investigator on the study.
- One study biostatistician that can be unblinded with regards to patient randomization, meaning that he/she is not involved in the statistical design, analysis and reporting of the study.
- Ad-Hoc members recruited to provide specific expertise and meet the Board's mandate.

Each DSMB member signed a Conflict of Interest Statement which includes current affiliations, if any, with pharmaceutical and biotechnology companies (e.g., stockholder, consultant), and any other relationship that could be perceived as a conflict of interest related to the study and / or associated with commercial interests pertinent to study objectives.

Data will continue to be presented in a blinded manner during the open sessions of the DSMB unless noted otherwise below. At DSMB meetings data and discussion are confidential. Participant identities will not be known to the DSMB members.

Mandate of the DSMB (defined in greater detail in the DSMB Charter):

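### The 90% power tied to the 462-patient cap at 4% vs 0% belongs to a fixed trial; under the plan's own interim rule it is about 58–61% (63–66% if futility is overridden)

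*Protocol*

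**What the plan says.** The initial sample size (Protocol Section 12.1) rests on "an effect size of 7% change (i.e. 7% in the control group vs. 0% in the investigational group", with at least 90% power, "using a two-tailed Fisher Exact test, with a nominal alpha of 0.05, a total sample size of 264 patients (132 per arm".

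Section 12.2 then sets the ceiling: "The maximum allowable sample size is set at 1.75 times the initial sample size (132 × 1.75 = 231 subjects per arm, or 462 in total". It links this ceiling to a 4% difference: "4% in the control group vs. 0% in the investigational group) using an alpha of 0.05 and 90% power".

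The interim look takes place "once 42% (112) of the planned 264 patients have either completed the Day 60 primary endpoint assessment" or left the study early (Section 7.2.1). For the lower edge of the promising zone, "the conditional power cut-off value (CPmin) is calculated as 38.6" per cent. From there up to 90% conditional power, the sample size is increased, at most to 462. At 90% or more the trial keeps 264. Under the lower edge, "If the conditional power is below the promising zone, the futility criteria will be deemed met", and a recommendation to stop enrolment goes to the DSMB.

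The Synopsis (Statistical Analysis) and Section 7.2.1 give the purpose: "To ensure the study is powered adequately if the effect size is smaller than initially estimated". The Synopsis design overview and the opening of Section 12.2 give similar assurances without mentioning a smaller effect. The only statement about the power of the adaptive rule is at the end of Section 12.2. It reports, without figures, that simulation showed slightly more power than a fixed design.

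**The concern.** The plan gives one power figure for an effect smaller than 7%, namely 90% at 4% vs 0%, and says the re-estimation secures adequate power in that situation. The figure belongs to a trial that always enrols 462. This trial enlarges only after an intermediate interim result. At a 4% control rate, 56 placebo patients yield 2.24 expected events (56 × 0.04), so 0 or 1 event is common. The rule then recommends stopping, even if LAU-7b prevents every event.

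Section 5.4.3.2 calls the extension confirmatory and a possible support for an emergency-use application. If the true control rate is near 4%, a futility stop or a non-significant result could be read as the failure of a trial with 90% power. On the plan's own rule the power was much lower.

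**Working it through.** **Inputs.** From Sections 7.2.1, 12.1 and 12.2: two-sided alpha 0.05, Fisher's exact test, 132 per arm initially, 231 per arm at most, interim at 112 patients, promising zone 38.6% to below 90%. Assumed: 56 per arm at the interim (1:1 allocation), LAU-7b rate 0%, complete data, conditional power from the normal approximation at the observed trend.

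**1. Reproduce the plan's figures.** With no LAU-7b events, 5 placebo events give Fisher p = 0.060 at 132 per arm and 0.061 at 231; 6 events give 0.029 and 0.030. So 6 or more placebo events are needed at either size.

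- 7% vs 0%, 132 per arm: P(Bin(132, 0.07) ≥ 6) = 90.6%.
- 4% vs 0%, 231 per arm: P(Bin(231, 0.04) ≥ 6) = 90.3%.
- 4% vs 0%, 132 per arm: P(Bin(132, 0.04) ≥ 6) = 43.4%.
- The lower edge of the promising zone computes to 38.5%, against 38.6% stated.

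Both stated sample sizes are correct as fixed designs.

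**2. Classify the interim results.** For k placebo events in 56 and none on LAU-7b, z = (k/56) / √[p̄(1 − p̄)(2/56)], with p̄ = k/112. For N per arm at the end and m = N − 56:

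CP(N) = Φ( z√(m/56) − [1.96√N − z√56]/√m ).

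Example, k = 2, N = 132: z = 1.427 and CP = Φ(1.662 − 1.358) = Φ(0.304) = 62%.

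| Placebo events at interim | CP at 132 per arm | Decision | Probability at 4% |
|---|---|---|---|
| 0 | 0.5% | futility | 10.2% |
| 1 | 29% | futility | 23.7% |
| 2 | 62% | promising | 27.2% |
| 3 | 83% | promising | 20.4% |
| 4 or more | 94% or more | stay at 264 | 18.5% |

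Futility totals 33.9% and the promising zone 47.6%.

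**3. Power at 4% vs 0%, futility followed.** Multiply each probability by the chance of reaching 6 placebo events in total at the resulting size.

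- 4 or more events, 132 per arm: 0.185 × 0.875 = 0.162.
- 2 events, 231 per arm: 0.272 × 0.922 = 0.251. CP at 231 is 86%, so the cap applies under either increase rule.
- 3 events, raised to 231 per arm: 0.204 × 0.973 = 0.198. Raised only until CP reaches 90% (164 per arm): 0.204 × 0.811 = 0.165.
- 0 or 1 event, stopped at 112 patients: cannot be significant, contributes 0.

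Always raised to 462: 0.162 + 0.251 + 0.198 = **61.1%**. Raised only as needed: 0.162 + 0.251 + 0.165 = **57.8%**. With futility followed, no increase rule or final test can exceed 1 − 0.339 = 66.1%.

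**4. Futility overridden, continuing at 264.** Add 0.102 × 0.084 + 0.237 × 0.188 = 0.053. Power becomes **63.1% to 66.4%**.

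**5. Other control rates, same method.**

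| Control rate (LAU-7b 0%) | Futility followed | Futility overridden |
|---|---|---|
| 4% | 58–61% | 63–66% |
| 5% | 73–75% | 80–82% |
| 6% | 84% | 90–91% |
| 7% | 90% | 95–96% |

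**6. Final test.** Section 12.7.1 names chi-square unless an expected cell is below 5. With equal arms the expected event count per arm is half the total, so chi-square applies only from 10 events up. With none on LAU-7b, Fisher is already significant there, so the results do not change.

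**The case against.** The strongest reply is that the sentence in Section 12.2 explains how the cap was chosen and does not state the power of the adaptive rule. That stands: the figure reproduces, and a reader who infers an arithmetic error in the 90% would be wrong. Section 12.2 also claims only slightly more power than a fixed design. That statement has no figure and no effect size attached, so it does not correct the impression left by the 4% and 90% pairing beside an assurance of adequate power.

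A second reply is that futility is a recommendation and nothing calls it binding. This also stands, and it matters: with futility overridden, power reaches about 90% at 6% vs 0%. At 4% vs 0%, the effect the cap is tied to, it still reaches only 63–66%.

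A third reply is that the rule is under-specified in the documents supplied. They do not give the conditional-power formula, the size of the increase within the promising zone, or the status of futility. The main SAP (29SEP2023) and the DSMB charter are cited but not supplied, and may contain operating characteristics. The result is sensitive: with exact plug-in Fisher conditional power and futility followed, power at 4% is 36%. The figures here are therefore indicative and should not be inserted as the plan's own.

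A reader might also infer that the re-estimation gives no protection against a smaller effect. The calculation does not support that: at 4% vs 0%, power rises from 43% with a fixed 264 to 58–61%.

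**Conclusion.** The concern holds as a matter of what is claimed. The 90% at 4% vs 0% is correct for a fixed 462 and is not a property of the interim rule. Under that rule, power at 4% vs 0% is about 58–61% with futility followed and 63–66% with futility overridden, about 25–30 points short. Protection against a smaller effect is partial: substantial at 6%, moderate at 5%, weak at 4%.

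The missing-data assumption deserves care. Protocol Table 3 counts missing outcomes as events, while the SAP Addendum (Section 2) analyses available data only. Neither document states a dropout rate, so complete data were assumed throughout.

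**What to change.** - In Section 12.2, state that 90% power at 4% vs 0% applies to a fixed trial of 462.
- In the same place, report the power of the full interim rule at 4%, 5%, 6% and 7% vs 0% from the sponsor's own simulation. State the conditional-power formula, the size of the increase within the promising zone, whether futility is followed, the final test, the LAU-7b rate and the handling of missing data. The table in step 5 can serve as a check on order of magnitude.
- In the Synopsis (design overview and Statistical Analysis), Section 7.2.1 and the opening of Section 12.2, replace the assurance of adequate power with a statement that the re-estimation increases power.

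The SAP Addendum records that results were first released on 14MAR2024, so the design's power cannot now change. The same statement belongs in the clinical study report, where the result will be interpreted. The cost is wording in four places, one reported table and a less favourable stated figure; no patients are added.
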